**Interventions:**

No formal interventions will be carried out during the course of this study. If clinically indicated, the participants (with their prior consent) will be referred to the Adult Audiology Services for further evaluation and hearing aiding assessment, or to the Ear, Nose and Throat (ENT), Audiovestibular Medicine (AVM) or Cochlear Implant Services at University College London Hospitals (NHS Foundation Trust) for further evaluation and management. The research student will seek formal advice from the Chief Investigator of the study before making the referrals. The referrals will be made following the participant's consent to do so and in accordance with the current clinical guidelines and with the protocol adopted at University College London Hospitals (NHS Foundation Trust). The participant's primary healthcare team/GP will be informed of the referral (with the participant's prior consent obtained to do so).

**Comparison:**

The findings obtained following the audiological and the quality-of-life questionnaires will be compared between the siderosis group, the ARHL group, and the control group. The results of vestibular assessments will be compared to the age-matched normative data.

**Outcomes:**

The outcomes will reflect the aims and objectives of the study. These will be recorded by the research student.

**Study/Participant Timeline:**

Following the Ethical approval to undertake the study, the relevant teams (team at the Neurology Department and the team at the Adult Audiology Services), University College London Hospitals (NHS Foundation Trust) will be informed by the research student of the study taking place. The potential participants will be identified by the relevant clinical teams (siderosis group and ARHL

group) and will be asked by the clinical team members for their consent to be contacted by the research student. To maximise the recruitment, the ARHL group will also be recruited from the general public. The control group will be recruited from the general public. We would like to recruit members of the general public aged 50 or above to closely approximate the age between the groups, however if such recruitment is difficult, we will recruit members of the general public aged 18 and above.

The recruitment will take place simultaneously for all three groups of participants. The recruitment period will be defined from the date the participant information sheet is sent to the potential participant to the participant giving formal consent to take part in the study. Potential participants interested in talking part in the study will be sent out the relevant study participant information sheet (group specific) together with the Data Use Confidentiality Statement and an Invitation Letter ahead of their first visit (to the University College London Hospitals (NHS Foundation Trust) or to the UCL Ear Institute). The first and follow-up visit for (potential) siderosis group participants will take place as part of their clinical appointment in the Neuro-otology Clinic. Additionally, a research appointment will be arranged. For participants from the ARHL and control groups the appointment/study visit will take place at either University College London Hospitals (NHS Foundation Trust) or the UCL Ear Institute, depending on the availability of the testing facilities. The date and time convenient for the participant and the research student will be determined in advance. During the initial/first consultation (siderosis group) /study visit (ARHL and control groups), the research student will obtain formal written consent from the participant and will document this in the medical notes and/or study file. A copy of the signed consent form will be given to the participant.

The research student and the participant (siderosis group participants only) will discuss the research visit and the tests that will take place then and whether the participant is willing to continue their participation in the research project. The research student will then arrange a suitable date/time for the research visit. The clinical follow-up visit will be scheduled by the clinical team and the interval will be decided as clinically necessary.

As a follow-up measure for the research study, all participants will be asked to complete a repeat (identical) set of questionnaires at a 12-month time interval after completing their first set. The identical set of questionnaires will be distributed to the participants by post with a pre-paid self-addressed envelope, or by email and will be returned by post or electronically.

The recruitment will take place over a 24-month period, the assessments and data collection will take place over a 36-month period. The last participant's follow-up appointment is anticipated to be no later than August 2021. The end of the study is defined when the last set of questionnaires is sent-out as a 12-month follow-up measure, whichever one of these events is last. The overall

study duration will be from August 2019 to (end of) July 2022 and will include the time required for data analysis and writing up of the results. Subsequent formal final study report will be put together for the Research Ethics Committee and the sponsor.

### **5.3 Data collection, management and handling**

Following the Ethical approval to undertake the study, the relevant teams (team at the Neurology Departments and the team at the Adult Audiology Services) University College London Hospitals (NHS Foundation Trust) will be informed by the research student of the study taking place. The potential participants will be identified by the relevant clinical teams (siderosis group and ARHL group), and contacted or approached in the clinical setting to ask permission to be contacted by the research student or to establish their decision to participate in the study and to be sent the study invitation letter and participant information sheets. The siderosis and ARHL group participants' contact details (including manual files that contain personal addresses, postcodes, e-mail and telephone numbers) will be kept secured in a locked folder by the participants' healthcare team at University College London Hospitals NHS Foundation Trust. Only the Chief Investigator and the clinical team members will have the key to the folder with the contact details for the participants. Once the participants are recruited onto the study, the participants' contact details (including personal addresses, postcodes, email or telephone numbers) will be kept on a secure UCL data safe haven platform (for participants from all groups).

The creation of coded, depersonalised data where the participant's identifying information is replaced by an unrelated sequence of characters to constitute a unique study ID number for each participant will be in place. No participant personal or identifiable data will be kept by the research student.

Secure maintenance of the data and the linking code in separate locations within lock folders and storage media will be ensured. The digital data collected by the research student will be stored in the UCL secure safe haven data platform with encryption and password protection.

### **5.4 Material/Sample Storage**

In the study, saliva sample will be collected from the siderosis group participants only (to the maximum of 30ml, i.e. the equivalent of the volume of maximum two table-spoons) in accordance with the patient consent form and patient information sheet.

Samples will be collected by the research student and will be anonymised. The samples will be labelled with a unique study code and will not contain identifiable information. The samples will be delivered by the research student to the designated laboratory in accordance with the UCL lab

protocol with which prior contractual agreement for processing and storage has been made. The samples will be stored for the duration of the study (three years). The samples will be processed, stored and disposed of in accordance with all applicable legal and regulatory requirements, including the Human Tissue Act 2004 and any amendments thereafter, and after relevant testing has taken place. Anonymised samples will be stored and used as part of this study but may be used for further testing in other/future studies.

The Chief Investigator will act as the custodian on behalf of UCL who is the data controller. The UCL Ear Institute Human tissue lab, London will store, process, and dispose of the samples.

## 5.5 Data analysis methods

Quantitative Analysis will be conducted using dedicated statistical software package.

Statistical analysis will be performed under the guidance and with advice of a designated biostatistician at UCL and/or at Biostatistics Office, UCL(H) Joint Research Office (JRO).

Each variable will be checked for distribution skewness, and regression models for each variable will be constructed. For binary variables, chi-square tests will be performed in order to determine the difference in the findings between the siderosis group and the control groups.

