We also hypothesise that there will be a greater deficit in speech-in-noise tests in iSS group compared with the ARHL and the control groups, when controlling for hearing deficits and that the speech-in-noise tests are better predictors of hearing dysfunction in iSS than PTA alone or with speech-in-quiet testing. We thus anticipate that speech-in noise tests will account for greater auditory deficits and will better correlate with patient-reported auditory difficulties than PTA and speech-in-quiet tests. We also anticipate a words-in-background babble test will be more able to predict auditory and cognitive impairment in iSS patients than a words-in-background speech noise.

Due to limited volume of literature that describes vestibular function in iSS and its heterogeneity in the battery of tests used, there is a need to provide a comprehensive description of vestibular function in these patients. We hypothesise that balance dysfunction will be due to a mixed (peripheral and central) vestibular deficits and that there will be a greater number of central and oculo-motor abnormalities detected in iSS patients when compared to normative data (40, 41). We also hypothesise that audiovestibular dysfunction will be identified in the majority of iSS patients after the initial radiological diagnosis and that these deficits will correspond to the involved structures of the auditory and vestibular pathways as visualised on brain images. Correlating the findings of assessments performed with the brain imaging would increase our understanding of the role of imaging in identification of the involved structure(s) of the audiovestibular pathways in iSS. Additionally, other clinical parameters may also be reflective of the symptom load or the degree of audiovestibular dysfunction and disease progression, and we would like to correlate the results of clinical tests performed in the clinical setting, including MRI, with the audiovestibular findings.

It is likely that iSS and its associated progressive and debilitating hearing and balance impairment) have a negative impact on quality of life. To our knowledge, this has not been reported in the literature and further studies are required to determine this. We will therefore assess the impact of iSS on the quality of life in patients with iSS.

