This will be one of the largest studies to date focusing on functional deficits in iSS, and will provide a detailed phenotype of its audiological and vestibular functions. The comprehensive test battery will allow to determine the accurate and disease-specific pattern of hearing and balance impairment in iSS. This in turn may lead to iSS being more frequently recognised, promptly diagnosed and timely initiation of treatment. In this study we will attempt to identify the tests that best measure functional impairment in iSS and can thus be used to assess the severity, and as a means of monitoring disease progression and the response to treatment. In addition, the study results will inform us regarding the most suitable and likely beneficial rehabilitative measures that can be offered to symptomatic patients with iSS in the clinical practice in the future.

This project will thus enhance our overall understanding and knowledge of hearing loss and imbalance, cognitive and olfactory functions in patients with iSS. By involving a larger cohort of patients which has previously been described by Wilson et al (7), we will be able to draw similarities with the reports evidenced in the literature and compare the findings to those of the age-matched individuals with ARHL and the control groups in the study. In addition, the use of comprehensive battery of hearing tests between the groups will help to determine tests that best identify and quantify auditory dysfunction. We will also be able to compare the results to the normative data and attempt to establish the impact of iSS on quality of life in comparison to individuals with age-related hearing loss and control group. This study will contribute to the global pool of knowledge regarding iSS and may improve understanding of this condition. This in turn may help inform research regarding means of diagnosis, management and rehabilitative measures, and monitoring of disease progression and treatment responses of audiovestibular dysfunction in iSS patients.

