#### 7.1.2 Age-related hearing loss (ARHL) group

Inclusion criteria:

- Adults (male and female) of 18+ years old with a known diagnosis of ARHL

Exclusion criteria:

- Individuals with a physical or mental impairment that prevents the potential participant from giving informed consent or undergoing the audiological assessment
- Individuals younger than 18 years old
- Individuals with diagnosis of hearing loss of aetiology other than age-related

- Individuals with history of exposure to high-intensity noise or ototoxic drugs or evidence of middle ear disease/dysfunction or family history of non age-related hearing loss
- Individuals with no previous diagnosis of age-related hearing loss

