### 7.1.3 Control group

Inclusion criteria:

- Adults (male and female) of 18+ years old with no previous diagnosis of hearing loss or no known neurological disorder (including iSS) that affects hearing (control group); we will aim to recruit such participants of 50 years of age and above, however if difficulty with recruitment of such participants arises, we will recruit participants of 18 years of age and above.

Exclusion criteria:

- Individuals with a physical or mental impairment that prevents the potential participant from giving informed consent or undergoing the audiological and assessment
- Individuals younger than 18 years old
- Individuals with a known history of hearing loss (of any cause) or with a known neurological disorder that affects their hearing
- Individuals with history of exposure to high-intensity noise or ototoxic drugs or evidence of middle ear disease or family history of non age-related hearing loss

Participants in the siderosis group will be users of the National Health Service (NHS) and will be recruited from University College London Hospitals (NHS Foundation Trust) London. The ARHL group participants will be recruited from the Adult Audiology Services at University College London Hospitals (NHS Foundation Trust), and will have used the NHS services in the past or will be recruited from the general public. The control group participants will be recruited from the general population. There will be no upper limit to the participants' age.

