#### Control group:

Potential participants will be recruited from the general public and will approximate the numbers of the participants in the siderosis group (20-30 participants). In order to best approximate the ages between the groups, we will aim to recruit general public participants of 50 years of age and above, however if difficulty with recruitment of such participants arises, we will recruit participants of 18 years of age and above. The study recruitment posters will be displayed in the public areas such as waiting areas, canteens and cafes in University College London Hospitals (NHS Foundation Trust) or by advertising the study and/or displaying study posters in community hearing aid centres, AgeUK, the University of Third Age, and through the BRC BioResource Bank at UCLH and dedicated Facebook/social network and online groups.

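### The comparators are called age-matched, but recruitment only approximates age, and the one test named for binary findings is a chi-square with no age adjustment

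*Combined protocol and SAP*

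**What the plan says.** All references are to the combined protocol and SAP.

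- **Rationale (section 2).** The study will "compare the findings to those of the age-matched individuals with ARHL and the control groups in the study". The speech-in-noise hypothesis predicts a "greater deficit in speech-in-noise tests in iSS group compared with the ARHL and the control groups, when controlling for hearing deficits".
- **Recruitment.** The Study/Participant Timeline (section 5.2) seeks members of the public "aged 50 or above to closely approximate the age between the groups, however if such recruitment is difficult", in which case the minimum drops to 18. Section 7.1.3 says the same of controls: "if difficulty with recruitment of such participants arises, we will recruit participants of 18 years of age and above". The ARHL criteria (section 7.1.2) admit "Adults (male and female) of 18+ years old with a known diagnosis of ARHL". Section 7.2.2 sizes the two comparator groups to match the siderosis group, up to 30 each. No procedure for matching on age is described.
- **Analysis (section 5.5).** After a skewness check, "regression models for each variable will be constructed. For binary variables, chi-square tests will be performed" to compare the siderosis group with the control groups. The section does not say whether that plural includes ARHL. It names no covariate or stratification factor. A biostatistician will advise.
- **Comparison (section 5.2).** Audiological and quality-of-life results are compared across the three groups. Vestibular results are compared with age-matched norms, so they fall outside this point.

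**The concern.** An age-matched design would remove much of the need to adjust for age. Here matching is claimed but no mechanism delivers it, so the analysis has to carry the adjustment. For binary findings the only test named cannot do so. The speech-in-noise hypothesis is conditional on hearing level, and an unadjusted contrast would answer a different question.

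What is at stake is how group differences are read: as a feature of iSS, or as a product of age or hearing level. It is not a formal error rate, because section 7.2.1 reports no power calculation and no gold-standard test.

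**Working it through.** The plan states no alpha, effect size or age gap, so there is no figure to reproduce. Only the group sizes (20 to 30, Study Summary) come from the documents. Every other input below is an assumption, including a two-sided 5% test and no true group effect.

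**1. Does the design deliver age matching?** The stated purpose in section 7.2.3 is approximation: "In order to best approximate the ages between the groups, we will aim to recruit general public participants of 50 years of age" and above, with the fallback to 18. All three groups are eligible from 18, and section 7.1.3 sets no upper limit. Group size is the only thing matched. The description in the Rationale is therefore not supported.

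**2. Can the direction of bias be worked out?** Bias = slope × difference in mean age. Assume a slope of 0.4 outcome SD per 10 years, and a quarter of controls recruited through the fallback, 20 years younger than the rest.
- If recruits aged 50 or over have the same mean age as the siderosis group, the bias is 0 without the fallback and 0.4 × (0.25 × 2) = +0.20 SD with it.
- If the siderosis group averages 10 years younger than those recruits, the bias is 0.4 × (−1) = −0.40 SD without the fallback and 0.4 × (−1 + 0.5) = −0.20 SD with it.

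The fallback adds bias in the first case and reduces it in the second. The Background says iSS can occur at any age but is often reported in middle-to-older patients. No ages are given, so the direction cannot be settled.

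**3. Binary findings.** Model: logit P = log(0.4/0.6) + log(OR) × x, where x is age in SD units with group means ±g/2. Chi-square = ((a − c)/n)² / (p(1 − p) × 2/n), where a and c are the two groups' counts and p is the pooled proportion, compared with 3.841 (20,000 runs). The adjusted test is a logistic likelihood-ratio test (2,000 runs, OR 2). Rejection rates:

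| Age gap g (SD) | Chi-square, n=20: OR 2 (OR 1.5–3) | Chi-square, n=30: OR 2 (OR 1.5–3) | Age-adjusted, n=20 | Age-adjusted, n=30 |
|---|---|---|---|---|
| 0 | 4.6% (4.4–4.6%) | 4.8% (4.7–5.0%) | 6.3% | 5.2% |
| 0.5 | 7.2% (5.8–9.9%) | 8.6% (6.5–13.5%) | 5.2% | 5.4% |
| 1.0 | 15.7% (8.6–26.4%) | 21.3% (11.2–38.6%) | 6.4% | 5.4% |
| 1.5 | 29.1% (14.1–50.8%) | 42.6% (19.3–70.9%) | 6.1% | 5.0% |

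A rarer finding gives a similar picture. Take 20% abnormal in the reference group and a 0.40 SD shift (age correlation 0.4, gap 1 SD). The other group then has Φ(Φ⁻¹(0.20) + 0.40) = Φ(−0.442) = 0.329 abnormal. Exact enumeration of the chi-square gives 15.5% (n=20) and 20.3% (n=30). Ordinary adjusted logistic regression gives 6.3% and 5.9%, and penalised logistic 4.3% and 4.8%. This is the reason for penalising when events are sparse.

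**4. Continuous findings, if the regressions were fitted without the covariate.** Section 5.5 does not say that they would be. Bias = r × g, where r is the correlation of outcome with covariate. With r = 0.3–0.5 and g = 1 SD, the bias is 0.30–0.50 SD. A t-test rejects in 16.0–33.0% (n=20) and 20.5–48.3% (n=30); with the covariate in the model, the rate over gaps of 0 to 1.5 SD is 4.2–5.7%. For speech-in-noise in iSS versus ARHL, r = 0.6 with PTA and a 0.5 SD hearing gap give 0.6 × 0.5 = 0.30 SD. The unadjusted test rejects in 15.2% and 20.8% (noncentral t, df 2n − 2), the PTA-adjusted test in 5.2% and 5.0%.

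**5. Precision after adjustment.** SE ratio = √((1 − r²)(1 + g²/4)).
- Age: from √(0.75 × 1.0625) = 0.89 (r 0.5, g 0.5) to √(0.91 × 1.5625) = 1.19 (r 0.3, g 1.5).
- PTA, iSS versus ARHL: from √(0.36 × 1.0156) = 0.60 (r 0.8, g 0.25) to √(0.75 × 1.1406) = 0.92 (r 0.5, g 0.75).
- PTA, iSS versus controls: an assumed gap of 2–3 SD multiplies the SE by √(1 + g²/4) = 1.41–1.80 through collinearity alone.

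The adjusted rates assume a correctly specified linear covariate effect with a common slope. They show what such a model achieves and are not a guarantee.

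**The case against.** The strongest reply is that section 5.5 plans a regression model for each variable under a biostatistician's guidance, and that the Rationale already frames the speech-in-noise hypothesis as controlling for hearing. Read together, adjustment is intended and regression is the tool; the chi-square may be an additional simple test. Much of this stands. Unnamed covariates are, on their own, missing detail and not a refusal to adjust, and the regression sentence could be read to cover binary variables. What remains is that chi-square is the only test named for binary findings and that the age-matched description is not met.

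Four stronger readings are tempting, but the documents do not support them.

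- **The 18+ fallback makes controls too young and exaggerates iSS effects.** This needs the siderosis age distribution, which is not given. Step 2 shows that the fallback can also reduce bias.
- **The 18+ floor leaves ARHL ages wide open.** This is weak: section 7.1.2 requires a known age-related diagnosis and excludes other causes, and the 50+ aim in the Timeline is worded for members of the public generally.
- **The pure-tone average should be the better ear, because the Background footnote defines disabling loss that way.** The right ear depends on how the test is presented, and section 5.2 says only that it is through headphones. Suppose the outcome follows the worse ear, with slope 0.6, gaps of 0.75 SD (worse) and 0.25 SD (better), and between-ear correlation 0.8. Unadjusted bias is 0.6 × 0.75 = 0.45 SD, and better-ear adjustment leaves 0.6 × (0.75 − 0.8 × 0.25) = 0.33 SD.
- **Adjustment settles every hearing comparison.** ARHL and control participants are selected on hearing status (sections 7.1.2 and 7.1.3), so an age-adjusted contrast in PTA itself still needs caution.

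**Conclusion.** The point holds in a limited form. The comparators are not age-matched by any procedure in the protocol, and the stated analysis of binary findings leaves between-group differences open to confounding by age. The regression models permit adjustment for age and PTA but do not commit to it, although the speech-in-noise hypothesis depends on hearing adjustment.

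The textual gap is certain. Its consequence is not: neither direction nor size can be derived from the documents. The illustrations show only that harm is negligible when the groups are close in age and grows materially once they differ by about 1 SD on a covariate that matters. This is worth correcting before analysis; it does not invalidate the study.

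**What to change.** In section 5.5:

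- Analyse binary between-group hearing findings by age-adjusted logistic regression, penalised if events are sparse. Keep chi-square results as descriptive only.
- Include age in the regression models for between-group comparisons of hearing tests and questionnaires.
- For speech-in-noise, make iSS versus ARHL the main contrast, adjusted for age and a pure-tone average. Fix its frequencies and ear or ears before analysis to fit how the test is presented, with the other ear as a sensitivity analysis. Treat PTA-adjusted contrasts with controls as secondary, because overlap in hearing level is likely to be poor.
- Do not adjust for PTA where PTA is the outcome, and state that age-adjusted PTA contrasts are read cautiously.

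In the Rationale, replace the age-matched description with: *of approximately similar age, with adjustment for age*. Report age and PTA by group. The recruitment rules need not change.

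The cost is wording and one or two model degrees of freedom. PTA is already measured in each ear in every group (section 5.2). Exact age is not listed as a study variable, since eligibility needs only 18 or over, but it will almost certainly be held; the protocol should say it is recorded. Some precision is lost if the age gap is wide (step 5 of the working). If many controls are much younger than the siderosis group, the result leans on the assumed form of the age effect.
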